## Seed-voxel Functional Connectivity Approach

A complementary approach to evaluate intrinsic connectivity involving seed-voxels from distinct brain regions will be performed using the functional connectivity "CONN" toolbox (Cognitive and Affective Neuroscience Laboratory, Massachusetts Institute of Technology, Cambridge,

CONFIDENTIAL 48 27 February, 2024

USA), version 15, running on Matlab R2017a (Whitfield-Gabrieli 2012). Pre-processed fMRI data from each participant are entered into the toolbox along with seed-voxel regions of interest, where time-series from each seed is extracted. White matter, cerebrospinal fluid (CSF) signal, and motion parameters are entered into the analysis as covariates of no interest. A band pass field (frequency window: 0.01 Hz to 0.1 Hz) will be applied in order to remove linear drift artifacts and high frequency noise. First level analyses will be performed by correlated seed-voxel signal with voxel signal throughout the whole brain, thereby creating seed region to voxel Fisher transformed r to z connectivity maps for each time point. These connectivity maps will be passed on to group level analysis and analyzed similar to those described in the Dual Regression ICA Approach section. While this approach can yield more focused inferences, there is some bias in choice of exact seed location and contour (Cole 2010). Thus, seeds will be carefully chosen based on the results of the evoked pain fMRI scan, with particular focus on insular clusters.

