# 3. Objectives and Endpoints

**Table 3: Study Objectives and Endpoints** 

| Objectives   | Endpoints   |
|--|---|
| Primary  |   |
| To assess the safety of TRP-8802 under the conditions of this trial  | Safety during dosing sessions: vital signs (HR, BP) (Section 8.1.1); AEs (Section 8.1.2),   |
|  | Safety during trial: AEs  |
| Secondary  |   |
| To evaluate the clinical benefit of oral TRP-8802 in concert with psychotherapy to treat chronic pain symptoms in patients with FM |   |
| To assess other potential therapeutic effects of TRP-8802 assisted therapy on FM symptoms  | Participant self-reported outcomes:  • pain interference (Section 8.2.1.2)  • sleep (Section 8.2.1.3)  • chronic pain acceptance (Section 8.2.1.4)  • Patient Global Impression of Change (PGI-C) (Section 8.2.1.5) |

| Objectives  | Endpoints  |
|-------------|--|
| Exploratory |  |
| •           | Patient reported outcomes relevant to chronic pain (Sections 8.2.2.1, 8.2.2.2)  • FM survey score, affect, catastrophizing, fatigue, anxiety, depression, cognitive impairment  Dosing-specific patient reported outcomes (Section 8.2.2.3)  • Mystical experiences  • Challenging experiences  • Psychological insight  Dosing-specific therapist reported outcomes  • Monitor rating scale (Section 8.2.2.3)  Qualitative written assessment (Section 8.2.2.4) to determine subjective participant experiences  Self-pain enmeshment (Section 8.2.2.5)  Self-complexity task (Section 8.2.2.6)  QST (Section 8.2.3.1)  • Change in cuff P40 pre- and post-intervention |
|             | 
 
Visual hypersensitivity
 
fMRI (Section 8.2.3.2)
 
Change in insula-default mode network connectivity
 
Change in Glx and/or GABA in anterior insula
 
Change in evoked pressure pain (tonic cuff)
 
Change in grey matter volume
 
Wrist actigraphy (Section 8.2.3.3)
 
Sleep onset latency
 
Wake after sleep onset
 
Total sleep time
 
Sleep efficiency (%)
 
  |

AEs=adverse events; BP=blood pressure; FM=fibromyalgia; GABA=gamma aminobutyric acid; Glx=glutamine+glutamate; HR=heart rate; P40=pain rating of 40 out of 100; PD=pharmacodynamic; QST=Quantitative Sensory Testing.

Note: The aggregate weekly pain score is over a 7-day period.

CONFIDENTIAL 23 27 February, 2024

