## **4.1.6.** End of Therapy (Visit 13, Day 64)

The EOT assessment will occur approximately 28 days after the last dosing session, when participants will complete their final deep phenotyping session. Regardless of whether or not a participant completes both dosing sessions or chooses to discontinue the study early, participants will be asked to complete all EOT and follow-up assessments if they have received at least 1 dose of TRP-8802.

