# 8.2.3.2. Functional Magnetic Resonance Imaging

Note: Participants who undergo MRI will meet all institutional guidelines and safety measures for MRI (e.g., no metal in the body, no claustrophobia, etc...).

The MRI sessions may include the following:

- structural MRI
- resting fMRI
- proton magnetic resonance spectroscopy (H-MRS) in the right anterior insula
- fMRI with tonic cuff pressure evoked experimental pain

Functional neuroimaging will include blood oxygenation level dependent (BOLD) fMRI at 3T using a T2\*-weighted gradient echo sequence on a General Electric MR750 Discovery MR system with a 32-channel head coil (University of Michigan Functional MRI Laboratory). The entire imaging session will take no more than 1 hour in total. Familiarization procedures will be completed prior to fMRI to reduce anxiety. Participants will be instructed that the neuroimaging can be stopped at any time if a procedure becomes unbearable. The fMRI assessment should take a total of approximately 55 minutes to complete and may include any of the assessments included in Table 6.

Table 6. Proposed Overview of Neuroimaging Visit fMRI Procedures

| Event  | Duration (mins) |
|--|-----------------|
| Structural   | 6               |
| Resting state fMRI (eyes open) – five 5-minute scans         | 25              |
|  H-MRS anterior insula (right)                   | 5               |
| Tonic cuff fMRI (eyes open) – left side – two 5-minute scans | 10              |
|  H-MRS anterior insula (right)                   | 5               |

<sup>1H-MRS=proton magnetic resonance spectroscopy; fMRI=functional magnetic resonance imaging

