## Functional Connectivity Magnetic Resonance Imaging

Functional connectivity MRI (fMRI) focuses on the default mode network (DMN) and salience network (SLN). The DMN is a constellation of brain regions engaged in self-referential cognition, which are "deactivated" during externally focused tasks (Buckner 2007, Fox 2007). Patients with more centralized pain display increased connectivity between the DMN and the insula (an SLN region [Menon 2015]) which is diminished with successful treatment (Napadow 2012). Whole-brain BOLD functional images will be acquired on the same 3 Tesla GE scanner described above, using a T2\* weighted echo-planar sequence. Parameters will be: TR/TE

CONFIDENTIAL 47 27 February, 2024

2040/30msec, flip angle=77°, FoV=240 mm, 33 AC-PC aligned slices, thickness 2.9 mm. Participants will rest comfortably in the scanner with eyes open for 25 minutes at the beginning of the scan session to obtain baseline measures of functional brain connectivity. Participants will be asked about current levels of pain intensity, fatigue and anxiety before and after resting state runs. Participants will also undergo two fMRI scans with tonic cuff pressure pain to evaluate functional brain connectivity response to deep pain. Pressure intensity will be set to each participant's Pain 30 to 50 level, as determined during the behavioral visit, and applied for 5 minutes for each scan. The pressure level from the behavioral visit will be verified prior to the scan initiation and re-calibrated in the event that it evokes more or less pain than anticipated. Pain intensity and unpleasantness ratings will be obtained at certain intervals during the test, up to three times and following stimulus presentation.

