## Dual Regression Independent Component Analysis Approach

The within-participant resting and cuff pain fMRI data analysis will be performed using the Group Independent Component Analysis (ICA) of fMRI Toolbox (GIFT) (Calhoun 2004). Intrinsic brain networks will be identified and quantified as component estimates. These components will then be validated using ICASSO software (Himberg 2004) for 10 iterations to ensure the reliability of ICA algorithm and to increase the robustness of the results. The number of independent components (networks) will be limited to 20 to 25 to minimize splitting into subcomponents. Participant-specific spatial maps and time courses will then be back reconstructed using spatio-temporal regression or dual regression options available in the toolbar, which ultimately creates a best approximation for each individual participant-specific Z-score component map. These Z-values reflect the degree of connectivity between each voxel and the group averaged time course of the component. To assure accuracy or know resting state networks, component maps will be identified with a spatial correlation using templates provided by previously published work (Smith 2009, Beckmann 2005). Individual resting state network maps will then be passed onto group second level analyses in SPM. Group analyses will be performed to evaluate intrinsic brain connectivity differences pre- and post-TRP-8802 treatment, how this intrinsic connectivity covaries with spontaneous pain intensity, and how networks differentially change following TRP-8802 treatment. The results will be thresholded at p < 0.001 voxelwise and p < 0.05, cluster-corrected for multiple comparisons.

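### Seeds for the exploratory connectivity analysis may be chosen from the trial's own cuff-pain scans, with no limit to Baseline and no correction across seeds

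*Combined protocol and SAP*

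**What the plan says.** Section 8.2.3.2, under Seed-voxel Functional Connectivity Approach, concedes that "there is some bias in choice of exact seed location and contour". Its answer is that "seeds will be carefully chosen based on the results of the evoked pain fMRI scan, with particular focus on insular clusters". It gives no coordinates, atlas, number of seeds, contrast or session.

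Four other places determine what that sentence can mean:

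- **Which scan.** The list of MRI procedures in Section 8.2.3.2 has one evoked-pain item, "fMRI with tonic cuff pressure evoked experimental pain". Its purpose is given under Functional Connectivity Magnetic Resonance Imaging: "Participants will also undergo two fMRI scans with tonic cuff pressure pain to evaluate functional brain connectivity response to deep pain".
- **When.** The Schedule of Activities (Table 2) marks fMRI at Baseline (Visit 2) and EOT (Visit 13). Section 4.1.6 confirms that at EOT "participants will complete their final deep phenotyping session".
- **Which endpoints.** Table 3 lists, as exploratory fMRI endpoints, "Change in insula-default mode network connectivity" and also the change in the tonic-cuff response.
- **Which test.** The seed maps go to a group analysis like that of the component (ICA) maps, where "Group analyses will be performed to evaluate intrinsic brain connectivity differences pre- and post-TRP-8802 treatment". The threshold there is p < 0.001 voxelwise and p < 0.05 cluster-corrected.

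Section 9.4.4 leaves the detail of exploratory endpoints to the SAP, which Section 9.4 requires before database lock.

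**The concern.** The plan recognises a source of bias and answers it with a choice made from trial data. The scan that supplies the seeds is also done after treatment, is described as a connectivity measurement, and is itself a change endpoint. So the text leaves room to pick the insular cluster whose cuff response moved most between visits, and then to test whether connectivity from that cluster changed between the same visits in the same people.

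Selection of that kind favours seeds with a large change. Cluster correction adjusts for the many voxels within one map. It does not adjust for having looked at several seeds and kept one. With about 10 participants and no control arm, chance differences between candidate seeds are large.

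What is at stake is limited but real. Section 9.2 says the study is meant to inform later trials, and Section 8.2.3.2 builds its rationale on insula-default mode connectivity falling with successful treatment. An inflated change could be carried forward as mechanistic support.

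**Working it through.** The plan gives no error rate, power or effect size for the seed analysis, so there is no figure to reproduce. What follows illustrates how much the selection route could matter.

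**From the protocol:** about 10 participants (Section 9.2); single arm (Section 4); within-person pre/post comparison; no stated correction across seeds.

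**Assumed, not in the documents:** K = 2, 5 or 10 candidate seeds; correlation between seeds of 0 or 0.5; correlation rho between a seed's cuff change and its resting change; two-sided test at 0.05 for each seed.

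**Step 1, worst case.** If selection and test use the same data (rho = 1), seeds are independent and the best is kept, the false-positive rate is 1 - 0.95^K:

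- K = 2: 1 - 0.95^2 = 0.0975
- K = 5: 1 - 0.95^5 = 0.226
- K = 10: 1 - 0.95^10 = 0.401

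**Step 2, selection on a different run.** Simulation under no true change: n = 10 and 40,000 runs, with a Monte Carlo standard error of about 0.001 near 0.05. For each seed, cuff change = rho × resting change + sqrt(1 - rho²) × independent noise. The seed with the largest |t| for cuff change is kept, and its resting change is tested by a paired t-test. Each cell gives the false-positive rate with between-seed correlation 0.5, then 0.

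| K | rho = 0 | rho = 0.3 | rho = 0.6 | rho = 1 |
|---|---|---|---|---|
| 2 | 0.050, 0.050 | 0.056, 0.056 | 0.066, 0.072 | 0.090, 0.097 |
| 5 | 0.049, 0.050 | 0.063, 0.068 | 0.099, 0.113 | 0.190, 0.227 |
| 10 | 0.050, 0.052 | 0.070, 0.074 | 0.125, 0.145 | 0.304, 0.400 |

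The last entries at rho = 1 agree with Step 1. At rho = 0 there is no inflation.

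**Step 3, size of the estimate.** Under no true change, the mean absolute standardised change of an unselected seed is 0.28. With independent seeds it becomes 0.30 to 0.37 for K = 5 and 0.31 to 0.41 for K = 10 at rho 0.3 to 0.6. At rho = 1 it reaches 0.57 and 0.70.

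**Step 4, selection that ignores the change.** If the seed is fixed in advance, or chosen independently of the pre/post change, the simulated rate is 0.049 to 0.051.

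**Step 5, Baseline-only selection on the tested measure.** If the seed kept is the one with the highest Baseline value of the same connectivity measure, regression to the mean remains. With test-retest correlation 0.5 to 0.8 and K = 2 to 10, the rejection rate is 0.048 to 0.088 and the mean spurious change is -0.04 to -0.25 SD. That is a fall, the direction which Section 8.2.3.2 associates with successful treatment.

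The simulation uses one test per seed and does not model the whole-brain cluster threshold.

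**The case against.** The strongest reply is that the protocol does not say seeds will be picked on treatment response. It refers to one scan, in the singular, without session or contrast. Using a pain scan to locate insular seeds for a separate resting analysis fits the wording, and if that is done at Baseline by a rule unrelated to the change, the error rate stays at 5%. This stands. A reader might infer that the connectivity estimate is biased; the text shows only that it could be.

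A reader might also take 23% or 40% as the likely error rate. Those figures need independent seeds and selection on the very data tested. Seeds close together in the insula, after 8 mm smoothing, are unlikely to be independent, and cuff and resting runs are different data.

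Two further inferences fail. Stable differences between people do not carry the bias, because they cancel in a within-person change; only correlated change between the two runs matters. Nor does the seed section say that the chosen seeds are then tested on the cuff runs: it speaks of intrinsic connectivity.

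Finally, the seed analysis is called complementary, the endpoint is exploratory, and the component analysis beside it is matched to published templates and needs no seeds. All of this limits the consequence. A SAP might fix the seeds, but no such text is in the document, and a deadline of database lock does not by itself come before the EOT scans are seen in an open-label study.

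**Conclusion.** The point holds as a gap in a stated selection rule. The plan lets insular seeds be chosen from the trial's own tonic cuff results without restriction to Baseline, without blinding to EOT data and without correction across seeds. If the choice follows post-treatment change, the pre/post insula-default mode result could be biased away from zero, with a false-positive rate above the nominal one.

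The size depends on two quantities that the documents do not give: the number of candidate seeds and the correlation between cuff change and resting change. For a correlation of 0.3 to 0.6, a nominal 5% becomes about 6-7% with 2 seeds, 6-11% with 5 and 7-15% with 10. The worst cases are 23% (5 seeds) and 40% (10 seeds). With no correlation there is no inflation.

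The point is minor. It touches one complementary analysis of an exploratory endpoint. The template-matched component analysis, the primary safety endpoints and the secondary endpoints are not affected.

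**What to change.** Amend the seed-voxel text in Section 8.2.3.2, and the SAP to match, before any EOT scan is analysed:

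1. Name the insular seeds by anatomical atlas region, or by published coordinates if the fibromyalgia connectivity work already cited reports them (this cannot be checked from the documents).
2. State how many seeds there are and correct across them as well as across voxels.
3. If trial data must be used, choose seeds from Baseline cuff scans only, under a written rule that is blind to EOT data and does not select on the Baseline connectivity measure that is later tested. Name the scan and session meant.

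Predefined seeds are preferable to item 3, because they also avoid the regression to the mean in Step 5.

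The cost is wording: no added scan, visit or participant. Seeds fixed in advance may fit this sample slightly less well, and correction makes each seed's test stricter, which is a reason to name few.

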## H-MRS Acquisition and Processing

H-MRS provides metrics amenable to longitudinal studies. High-resolution anatomical scans isolate identical brain structures within individuals over time thus minimizing error that otherwise would occur because of slight differences in voxel location from one evaluation to the next. Previous H-MRS studies have utilized this approach to examine changes in the levels of central nervous system metabolites in test-retest studies (Evans 2010). H-MRS will be focused on the right posterior insula cortex both prior to and following evoked cuff pressure pain. The right and left sides of the brain are chosen, as this these areas have been shown to be involved in chronic FM pain (Harris 2009, Harris 2008). H-MRS studies will be performed on the same 3 Tesla GE system as for fMRI. Details of the H-MRS methods are presented in previously published work (Harris 2009, Harris 2008). Single voxel MRS will be performed on the right anterior insula with a voxel size of 2 x 3 x 3 cm. The H-MRS scanning protocol will be PRESS TR/TE=2000/35 ms with and without water suppression with 64 averages and a total scan time of approximately 5 minutes. The water signal will be recorded using 8 averages (scan time 16 seconds). Participants will be at rest during the H-MRS session.

The raw data will undergo manual post-processing using H-MRS software (LCModel; Stephen Provencher, Oakville, Ontario, Canada). LCModel uses a linear combination of individual spectra obtained from pure molecular species to fit the experimental spectra (Provencher 2001). Values for Glx (glutamine+glutamate) will be calculated as ratios to total creatine as well as absolute concentrations using the water signal for normalization. Resulting metabolite absolute concentrations will be reported in arbitrary institutional units. Since the voxels used incorporate CSF, and the volume of CSF dilutes H-MRS-derived metabolite values, metabolite levels for CSF volume for each participant will be corrected as reported previously (Harris 2009). Voxel Based Morphometry, a toolbox that operates within the image analysis program SPM, Functional Imaging Laboratories, London, UK) will be used.

## Feasibility of H-MRS Approach

All of the H-MRS procedures outlined above have been successfully implemented (Mawla 2021, Harris 2009, Harris 2008). These studies suggest that changes in Glx and gamma aminobutyric acid (GABA) within the posterior and anterior insula are strongly correlated with improvements in pain, with reductions in clinical pain being associated with lower Glx and higher GABA levels.

CONFIDENTIAL 49 27 February, 2024

# 8.2.3.3. Wrist Actigraphy

Wrist actigraphy is a method of longitudinal sleep tracking in the ambulatory environment. Wrist actigraphy via the Fitbit Charge 5 or Actiwatch Spectrum (Philips Respironics) will be used. Actigraphy will be conducted among all participants to identify changes in sleep associated with TRP-8802 and psychotherapy treatment.

Objective measures of total sleep time (sleep duration), wake after sleep onset (sleep continuity), and sleep timing (sleep onset and wake time) will be assessed with wrist actigraphy. Participants will be trained to use actigraphic devices and will also complete a sleep log (0 to 10 NRS daily sleep quality, time in bed, number of wake times, final wake time, estimated sleep onset) via the actigraphic device as well as a paper diary every morning during actigraphy for additional validation (Burgess 2010a, Burgess 2010b). Data extraction, cleaning, and analysis will be performed using the proprietary algorithm provided by the manufacturer.

# 8.3. Other Safety Assessments

## 8.3.1. Electrocardiograms

For screening purposes only, a single 12-lead ECG will be obtained at the Screening visit using an ECG machine that automatically calculates the HR and measures PR, QRS, QT, and QTc intervals. Participants will be supine and rested for approximately 5 minutes before the ECG is recorded.

Screening ECGs will be read locally by the Principal Investigator for determination of meeting study entry criteria.

## 8.3.2. Pregnancy Testing

A urine pregnancy test will be performed, and results will be determined locally. Pregnancy test results must be negative at Screening, before TRP-8802 is administered on drug session days, and before fMRI is performed.

## 8.3.3. Urine Drug and Breath Alcohol Testing

The urine drug screen will be performed locally to detect tricyclic antidepressants, amphetamines, methamphetamine, MDMA (ecstasy), phencyclidine, barbiturates, benzodiazepines, cocaine, cannabis, and opioids, including opiates, oxycodone, and methadone. A breathalyzer will be used to estimate the blood alcohol content.

At Screening, participants who test positive for cocaine, methamphetamine, or opioids will be excluded from the study.

On drug session days, drug (excepting cannabis) and alcohol test results must be negative (blood alcohol content of less than 0.02% [verified with a second test]) before TRP-8802 is administered. If a participant does not have a negative result, they will be given a chance to reschedule (within the allowed window). A second failure will result in the participant's study termination.

CONFIDENTIAL 50 27 February, 2024

# 8.4. Adverse Events, Serious Adverse Events, and Other Safety Reporting

The definitions of AEs and SAEs can be found in Appendix 2, Section 10.2.1 and Section 10.2.2, respectively. Adverse event grading will be performed using the Toxicity Grading Scale for Healthy Adult and Adolescent Volunteers Enrolled in Preventive Vaccine Clinical Trials (US FDA Guidance for Industry 2007).

The investigator and any qualified designees are responsible for detecting, documenting, and recording events that meet the definition of an AE or SAE and remain responsible for following AEs that are serious, considered related to the study intervention or study procedures, or that caused the participant to discontinue the study (Section 7). During dosing sessions, manifestations of the psychedelic experience will not be recorded as AEs unless judged by the therapists to exceed the intensity and/or duration of expected reactions.

